#### **9.4.3 Secondary endpoint(s) in Part A**

The key secondary efficacy endpoints include the CAFS at Week 24, and change from baseline in SVC, change from baseline in muscle strength, ALSAQ-5, and serum NfL to Week 24. All secondary efficacy endpoints will be analyzed based on the ITT population.

For continuous variables, an MMRM approach under the MAR assumption will be used. This model will include the fixed effect of treatment (SAR443820 or placebo), visit as a categorical variable, baseline value of the endpoint, baseline NfL (if different from the baseline value of the endpoint), randomization strata of the geographic region of the study site, ALS onset region (bulbar or other areas), use of riluzole (yes or no), use of edaravone (yes or no), use of the combination of sodium phenylbutyrate and taurursodiol (yes vs no), treatment-by-visit interaction, and baseline value of the endpoint-by-visit interaction and baseline NfL-by-visit interaction (if different from the baseline value of the endpoint-by-visit interaction). The primary comparison of interest will be the difference between SAR443820 and placebo at Week 24, carried out using contrast within the treatment-by-time interaction term. Available data will be used for all secondary analyses.

To have strong control of the Type I error rate, a closed sequential testing approach will be used. The order of the secondary efficacy endpoints and all the details of sequential testing will be specified in the full SAP. The details of the analysis for other secondary endpoints will be outlined in the full SAP.

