	Change from baseline in slow vital capacity (SVC) (muscle strength, Amyotrophic Lateral Sclerosis Assessment Questionnaire (ALSAQ-5), serum neurofilament light chain (NfL)) to Week 24	ITT	Permanent study intervention discontinuation before Week 24 – regardless of treatment discontinuation (treatment policy)		These secondary endpoints will be analyzed using MMRM with change from baseline value up to Week 24 as response variable, and treatment, visit, randomization strata of the geographic region of the study site, ALS onset region (bulbar or other areas), use of riluzole (yes or no), use of edaravone (yes or no), use of the combination of sodium phenylbutyrate and taurursodiol (yes or no), treatment-by-visit interaction, disease duration (from first symptom onset to the screening visit), baseline value of the endpoint, baseline NfL (if different from the baseline value of the endpoint), disease duration-by-visit interaction, baseline value of the endpoint-by-visit interaction and

Endpoint Category (estimand)	Endpoint	Population	Intercurrent event(s) handling strategy	Estimands	Population-level summary (Analysis and missing data handling)
				baseline NfL-by-visit interaction (if different from the baseline value of the endpoint-by-visit interaction) as covariates. All available data will be used, and missing data will be handled by MMRM based on missing at random assumption. For muscle strength data, if there is a missing value for one muscle measurement which continues to have the missing value through the final assessment (eg, at least 2 consecutive missing values up to the final assessment), then these missing values for this muscle measurement will be imputed as zero; all the other missing values will not be imputed.	

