3.2.2 Main analytical approach

Part A

The primary endpoint in Part A will be analyzed with the estimand defined according to the following attributes:

- Endpoint: Change from baseline in the ALSFRS-R total score to Week 24
- Treatment condition: SAR443820 will be compared to placebo
- Analysis population: ITT population
- Intercurrent events (IE):
 - The IMP discontinuation IE will be handled with the treatment policy strategy; The primary endpoint will be assessed based on all assessments irrespective of the IMP discontinuation
- Population-level summary: The primary endpoint will be analyzed using MMRM with change from baseline in ALSFRS-R total score up to Week 24 as response variable, and treatment, visit, randomization strata of the geographic region of the study site, ALS onset region (bulbar or other areas), use of riluzole (yes or no), use of edaravone (yes or no), use of the combination of sodium phenylbutyrate and taurursodiol (yes or no), treatment-by-visit interaction, disease duration (from first symptom onset to the screening visit), baseline ALSFRS-R score, baseline NfL, disease duration-by-visit interaction, baseline NfL-by-visit interaction and baseline ALSFRS-R score-by-visit interaction as covariates. If less than 10 participants in a randomization strata level, then the corresponding factor will not be included as a covariate in the MMRM model.

The least squares mean difference in the ALSFRS-R change from baseline at Week 24 between SAR443820 vs placebo, together with the p-value and the 95% CI for the difference, will be estimated from the MMRM model using weights for each stratum equal to the overall proportion of participants in each stratum (ie, “population weight”) by inclusion of the OBSMARGINS option in the LSMEANS statement. Plots of least squares means (\pm standard error) over time will be provided.

This model will be implemented using the SAS MIXED procedure with an unstructured covariance matrix to model the within-participant errors. Parameters will be estimated using the restricted maximum likelihood method. The denominator degrees of freedom will be estimated using the Kenward-Roger approximation. This model will provide baseline adjusted least-squares means estimates at Week 24 for SAR443820 and placebo, together with their corresponding standard errors and CIs. If this model fails to converge, the following variance-covariance structures will be tested in this order:

- Heterogeneous Toeplitz
- Heterogeneous AR(1)

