3.3.1.2 Main analytical approach

Treatment policy will be used for the analyses of all secondary endpoints in Part A and Part B as stated in [Table 2](#).

CAFS

CAFS at Week 24, Week 76 and Week 104 will be analyzed in the same manner as that used to analyze the primary endpoint in Part B in [Section 3.2.2](#).

Continuous Endpoints

Continuous endpoints include:

Part A

- change from baseline in SVC to Week 24
- change from baseline in muscle strength to Week 24
 - change from baseline in megascore to Week 24
 - change from baseline in grip strength to Week 24
- change from baseline in ALSAQ-5 to Week 24
- change from baseline in serum NfL to Week 24

Part B

- change from baseline in the ALSFRS-R total score to Week 52, Week 76, and Week 104
- change from baseline in SVC to Week 52, Week 76, and Week 104
- change from baseline in ALSAQ-5 to Week 52, Week 76, and Week 104
- change from baseline in serum NfL to Week 52

These continuous endpoints will be analyzed using the same manner as that used to analyze the primary endpoint in Part A in [Section 3.2.2](#), except that baseline ALSFRS-R score will be replaced by the baseline value of the corresponding endpoint. Plots of least squares means (\pm standard error) over time will be provided. Plots of mean (\pm SD) and/or mean change (\pm SD) and/or median over time will also be provided. For NfL data, log transformation will be applied in

the MMRM model. The treatment difference will then be back-transformed to the original scale. The back-transformed LS means stand for geometric mean ratios compared to baseline, and the back-transformed LS means difference stands for ratio of the geometric mean ratios compared to baseline between SAR443820 and placebo. In order to assess the impact of deviation from the normality assumption, a sensitivity analysis using rank analysis of covariance (ANCOVA) with the same covariates as for the MMRM analysis except visit and related interaction terms, will be performed to provide the p-value for the comparison between the treatment groups.

Time-to-event endpoints

Time-to-event endpoints in Part B include:

[figure not shown]
- time from baseline to occurrence of either death or permanent assisted ventilation (>22 hours daily for >7 consecutive days), whichever comes first
- time from baseline to the occurrence of death

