3.5 MULTIPLICITY ISSUES

To control the Type 1 error rate for the study, a hierarchical testing procedure will be applied at a 2-sided 5% significance level for primary and selected secondary endpoints in Part A, ie, each hypothesis will be formally tested only if the preceding one is significant at the 5% level. If

SAR443820 is significant for the primary endpoint in part A, a selective set of secondary endpoints in Part A will be tested following the hierarchical testing procedure shown below:

- CAFS score at Week 24
- Change from baseline in ALSAQ-5 to Week 24
- Change from baseline in serum NfL to Week 24
- Change from baseline in SVC to Week 24
- Change from baseline in megascore to Week 24

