5.3 APPENDIX 3 DEMOGRAPHICS AND BASELINE CHARACTERISTICS, PRIOR OR CONCOMITANT MEDICATIONS

Demographics, baseline characteristics, medical surgical history

The following demographics and baseline characteristics, smoking and alcohol history, medical and surgical history and disease characteristics at baseline will be summarized using descriptive statistics in the randomized population.

Demographic and baseline characteristics include:

- age in years as quantitative variable and in categories (< 65, \geq 65)
- gender (Male, Female)
- race (White, Black or African American, Asian, American Indian or Alaska Native, Native Hawaiian or Other Pacific Islander, Multiple, Unknown, Not reported)
- ethnicity (Hispanic or Latino, not Hispanic or Latino, Unknown, Not reported)
- region (US, non-US; North America, Europe, Asia)
- weight in kg as a quantitative variable
- BMI in kg/m² as a quantitative variable and in categories (< 25, \geq 25 to $<$ 30, \geq 30)

Smoking and alcohol habits:

- smoking history (Never, Current, Former)
- cessation prior to screening for Former smokers in months
- cigarettes per day for smokers
- frequency of alcohol drinking in the past 12 months (Never, Occasional, At least monthly, At least weekly, At least daily)
- Number of standard alcohol drinks on typical day when drinking (1 or 2, >2)

Disease characteristics at baseline include:

- ALS diagnosis type (possible, clinically probable ALS, clinically probable laboratory-supported, or clinically definite)
- initial disease onset location (bulbar, other)
- ALS disease duration (years) from first symptom onset to the screening visit
- time since diagnosis (years)
- ALSFRS-R total score
- ALSFRS-R pre-study slope defined as (48-ALSFRS-R score at the screening visit)/duration in months between the screening visit and disease onset)
- SVC

- use of Riluzole collected from IRT
- use of Edaravone collected from IRT
- use of the combination of sodium phenylbutyrate and taurursodiol collected from IRT
- use of Riluzole and Edaravone collected from IRT
- use of Riluzole and the combination of sodium phenylbutyrate and taurursodiol collected from IRT
- use of Edaravone and the combination of sodium phenylbutyrate and taurursodiol collected from IRT
- use of Edaravone and the combination of sodium phenylbutyrate and taurursodiol collected from IRT

Baseline safety and efficacy parameters (apart from those listed above) will be presented along with the safety and efficacy summaries.

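### The four gated continuous secondary models use the endpoint's own baseline in place of baseline ALSFRS-R; keeping both would cost almost nothing and could modestly improve precision

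*SAP*

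**What the plan says.** - **Primary model (SAP 3.2.2).** Besides treatment, visit, their interaction and the stratification factors, the model has "disease duration (from first symptom onset to the screening visit), baseline ALSFRS-R score, baseline NfL, disease duration-by-visit interaction, baseline NfL-by-visit interaction" and a baseline ALSFRS-R-by-visit interaction.
- **Continuous secondary endpoints (SAP 3.3.1.2).** The same model applies, "except that baseline ALSFRS-R score will be replaced by the baseline value of the corresponding endpoint". Table 2 in SAP 1.2.1 agrees, listing "baseline value of the endpoint, baseline NfL (if different from the baseline value of the endpoint), disease duration-by-visit interaction".
- **Gated tests (SAP 3.5).** After the primary endpoint the order is CAFS, ALSAQ-5, NfL, SVC and finally "Change from baseline in megascore to Week 24". CAFS has a Wilcoxon-type test, so the other four are the ones affected.
- **Part B time-to-event endpoints (SAP 3.3.1.2).** The Cox models hold disease duration, baseline ALSFRS-R and baseline NfL together.
- **Protocol 9.4.3.** The continuous secondary model has "baseline value of the endpoint, baseline NfL (if different from the baseline value of the endpoint") and no baseline ALSFRS-R. It has no disease duration either; the SAP adds that.
- **Progression rate.** SAP Appendix 3 has "ALSFRS-R pre-study slope defined as (48-ALSFRS-R score at the screening visit)/duration in months between the screening visit and disease onset" as a baseline characteristic, and inclusion criterion I 04 uses the same quantity. It is a covariate in none of these models.

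**The concern.** Pre-study slope is built from two quantities, ALSFRS-R and time since onset. A model that holds both baseline ALSFRS-R and disease duration comes close to holding the slope. A model that holds duration without ALSFRS-R does not, because duration says little about rate unless the function lost over that time is known.

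The SAP treats baseline ALSFRS-R as prognostic beyond its own change score, since it keeps the term in the Part B Cox models. It gives no reason for leaving the term out of the continuous secondary models. The score is scheduled for every participant at screening and Day 1.

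At stake is precision in four confirmatory tests, in a hierarchy where a miss on one blocks those after it. ALSAQ-5 comes first of the four. A weaker covariate set may also make missing-at-random somewhat less plausible in these MMRMs. The NfL model is the thinnest: its own baseline is NfL, so it contains no functional score at all.

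**Working it through.** **1. The plan's own figure.** SAP 4 gives N = 261 (174:87 at 2:1) for about 80% power, two-sided 5%, 20% drop-out, for the primary endpoint only. The placebo change and SD are redacted and N came from simulation, so 261 cannot be reproduced. Inverting a two-means approximation for 139.2 and 69.6 completers gives

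δ/SD = (1.960 + 0.842) × √(1/69.6 + 1/139.2) = 2.802 × 0.1468 = 0.411.

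This serves below only as an illustrative effect size. The documents state no power for any secondary endpoint.

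**2. How much of the pre-study slope each covariate set captures.** Simulated population; every input is an assumption: duration uniform over 6 to 24 months; log-normal slope with median 0.8 points/month and log-SD 0.5; ALSFRS-R = 48 − slope × duration + noise (SD 1.5); observed slope at least 0.5 (I 04) and ALSFRS-R above 15; correlation of log slope with NfL 0.2 to 0.6; correlation of baseline ALSFRS-R with the endpoint's own baseline 0.3 to 0.7.

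| Covariates | R² for pre-study slope |
|---|---|
| Duration + ALSFRS-R + NfL (as in the primary model) | 0.88 |
| Duration + own baseline + NfL (ALSAQ-5, SVC, megascore) | 0.10 to 0.48 |
| Duration + NfL (the NfL model) | 0.06 to 0.31 |
| Duration alone (no model in the SAP) | 0.03 |

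The secondary models adjust for rate in part, less fully than the primary model.

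**3. What adding ALSFRS-R removes from residual variance.** Let r be the correlation between progression rate and the Week 24 change. If rate is the only route by which these baselines predict that change, the proportional reduction is approximately

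r² × (R²_with − R²_without) / (1 − r² × R²_without).

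| r | R²_without = 0.105 | R²_without = 0.262 | R²_without = 0.482 |
|---|---|---|---|
| 0.1 | 0.8% | 0.6% | 0.4% |
| 0.2 | 3.1% | 2.5% | 1.6% |
| 0.4 | 12.6% | 10.4% | 7.0% |

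Here R²_with is 0.882, 0.882 and 0.884. Example, middle column at r = 0.2: 0.04 × 0.620 / (1 − 0.04 × 0.262) = 0.0248/0.9895 = 2.5%. A separate large-sample regression calculation gave about 0.5% at r = 0.1 and 2% to 10% at 0.2 to 0.4, which agrees in order of size.

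**4. In participants and power.** A variance reduction v is worth 261 × v/(1 − v) participants: 5 at v = 0.02 and 29 at v = 0.10. A hypothetical test with 80% power moves to Φ(2.802/√(1 − v) − 1.960): 81% at v = 0.02, 84% at v = 0.10, and 80.2% at v = 0.005.

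**5. Simulation check.** Single-visit ANCOVA, 139 against 70 completers, 4,000 runs per cell, assumed effect 0.411. The three rows within each r run from weak to strong correlations of NfL and own baseline with disease status.

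| r | SE, SAP model | SE, ALSFRS-R added | Power, SAP model | Power, ALSFRS-R added |
|---|---|---|---|---|
| 0.3 | 0.1468 | 0.1424 | 78.9% | 82.0% |
| 0.3 | 0.1456 | 0.1422 | 81.7% | 83.5% |
| 0.3 | 0.1441 | 0.1422 | 81.6% | 82.8% |
| 0.5 | 0.1457 | 0.1319 | 79.9% | 87.3% |
| 0.5 | 0.1427 | 0.1321 | 83.1% | 87.4% |
| 0.5 | 0.1380 | 0.1318 | 84.3% | 87.6% |

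At r = 0.3 the standard error falls by 1.3% to 3.0% and power rises by about 1 to 3 points. The r = 0.5 rows lie above the range used for the conclusion. Type I error was 4.8% to 5.4% without ALSFRS-R and 4.5% to 5.4% with it; Monte Carlo error is about 0.3 points.

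**The case against.** **These models are standard and match the protocol.** Adjusting a change score for its own baseline is normal practice, and protocol 9.4.3 never had baseline ALSFRS-R in these models. A reader might infer from the SAP's wording that a protocol covariate was deleted. It was not: the SAP's wording is shorthand, and relative to the protocol the SAP adds disease duration. This stands.

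**Adjustment for progression rate is not lost.** A reader might also infer that these tests have no adjustment for rate. The documents do not support that. Baseline NfL, which SAP 3.3.1.1 itself associates with fast progression, stays in all four models. Own baseline is a severity measure for ALSAQ-5, SVC and megascore. The primary model has no explicit slope term either. This stands too.

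**The magnitude is assumed.** The documents give no correlations and no power for these endpoints. SAP 3.3.1.1 describes NfL as stable over time in ALS, so a link between NfL change and prior rate cannot be presumed. This also stands, and it is why the gain is given as a range that reaches almost zero.

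**Missing data.** No passage says drop-out from these assessments follows global function. What is documented is that after early IMP discontinuation Part A footnote b keeps ALSFRS-R, SVC and NfL but not ALSAQ-5 or muscle strength, and that persistently missing strength values are set to zero. A baseline covariate cures neither. The missing-at-random argument is therefore only supporting.

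**Late change.** SAP version 1 preceded a futility analysis that uses NfL change, so altering the confirmatory NfL model now needs justification. That is reasonable, but the added term is a pre-randomisation covariate, and the current SAP was itself approved before the first database lock.

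**Existing sensitivity analyses.** The rank ANCOVA for these endpoints uses the same covariates as the MMRM, so it does not bring ALSFRS-R back. The text of SAP 3.2.3 is not visible, so a further analysis there cannot be excluded.

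**Conclusion.** The point holds as a low-cost improvement in precision. The four gated continuous secondary models adjust less fully for severity and progression rate than the primary and Cox models, and no visible text supplies the missing term. Randomisation protects the comparison and type I error stays near 5% with or without the term, so nothing here undermines the validity of the tests.

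The likely gain is about 0.5% of residual variance if progression rate correlates 0.1 with change in the endpoint, and about 2% to 10% at 0.2 to 0.4. For NfL it may be nil. These figures rest on the assumed distributions and correlations in the working, on a single-visit approximation to the MMRM, and on a notional 80% power that the plan claims only for its primary endpoint.

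**What to change.** Before database lock and unblinding:

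1. In SAP 3.3.1.2, change *replaced by* to *supplemented by*. Baseline ALSFRS-R and its by-visit interaction then stay in the model next to the endpoint's own baseline and its by-visit interaction. Add an if-different clause, as the SAP already does for NfL, because in the Part B ALSFRS-R model the two are the same variable.
2. Add the same two ALSFRS-R terms to the covariate list in the continuous-secondary row of Table 2.
3. Record the change in SAP 3.9 as a departure from protocol 9.4.3, stating that it was made without access to unblinded results.

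Pre-study slope with its by-visit interaction would serve about as well; choose one in advance.

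The cost is one parameter per visit in each model, one covariate in each program and a SAP amendment. No new data are needed. The rank ANCOVA sensitivity analysis picks up the term automatically because it borrows the MMRM covariates. The ALSAQ-5 and strength data not collected after early IMP discontinuation are a separate matter that this change leaves as it is.

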### **3.1 APPROPRIATENESS OF MEASUREMENTS**

#### **3.1.1 Measurements for efficacy assessment**

The primary endpoint of this study is the change of ALS disease progression as measured by the ALSFRS-R, which is a validated and established outcome measurement of therapeutic efficacy for ALS. The ALSFRS-R is a widely accepted measure of ALS progression used by clinical trialists and regulatory bodies (14).

[figure not shown]
The CAFS is a measurement ranking the clinical outcomes of patients with ALS based on survival time and change in the ALSFRS-R score (15). The combined endpoint can decrease the confounding effect of mortality on the results of an analysis of functional outcomes as it appropriately accounts for and weights mortality in the analysis of function.

For the survival assessment, in addition to mortality, a composite time-to-event endpoint recording the time to death or permanent continuous ventilator dependence, whichever occurs first, will be assessed as 1 of the efficacy endpoints since survival data may be confounded by the use of ventilation strategies. This approach is consistent with guidance from the FDA and European Medicines Agency (EMA) (14, 16).

The SVC percentage of predicted normal provides a quantitative means to assess reductions in the strength of the diaphragm and other respiratory muscles. The SVC change over time has been demonstrated to be associated with meaningful clinical events, including the time to respiratory insufficiency or death (17).

Muscle weakness is a typical feature of ALS and an important determinant of participants' daily function and QoL. Handheld dynamometry provides a quantitative means to assess limb muscle strength.

The ALSAQ-5 has been demonstrated to be a sensitive and reliable instrument for estimating QoL in patients with ALS (18) and provides similar results to the ALSAQ-40 but with a considerable reduction in patient burden (19).

.....

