For the time-to-event endpoints, baseline is defined as randomization. The time to event will be modeled by a Cox proportional hazards model. The covariates included in the model are treatment group, randomization strata of the geographic region of the study site, ALS onset region (bulbar or other areas), use of riluzole (yes or no), use of edaravone (yes or no), use of the combination of sodium phenylbutyrate and taurursodiol (yes or no), disease duration (from first symptom onset to the screening visit), baseline ALSFRS-R score and baseline NfL. The hazard ratio between SAR443820 and placebo, its 95% confidence interval and the p-value for comparing SAR443820 and placebo will be estimated from this model with robust variance estimation (9). Comparison between SAR443820 and placebo will also be assessed by a log-rank test stratified by randomization strata of the geographic region of the study site, ALS onset region (bulbar or other areas), use of riluzole (yes or no), use of edaravone (yes or no), use of the combination of sodium phenylbutyrate and taurursodiol (yes or no) and baseline NfL (< median baseline NfL or >= median baseline NfL). Kaplan-Meier (KM) plots of the cumulative incidence rate will be provided by treatment group to depict the course of occurrence of event over time. The proportion of participants with events at given time points (eg, Week 4, 8, 12, 16, 20, 24, etc.) and median time to event (if feasible) will be calculated using the KM estimates.

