3.4.3 Comparison with external control

A matched analysis using data from historical clinical trial database (for example, PROACT) as a control will be conducted to demonstrate the superiority of SAR443820 on slowing down disease progression and prolonging survival over 104 weeks of treatment period.

Matching procedure

1. Pre-matching filtering: The participants in the historical clinical trial database will be filtered by the following factors that match our trial eligibility criteria and duration:
 - Age 18 – 80 years, inclusive
 - First ALS symptom onset ≤ 2 years
 - Baseline SVC (%) $\geq 60\%$
 - Baseline ALSFRS-R decline rate $\geq 0.5/\text{month}$
2. Propensity score matching: Propensity score matching seeks to balance the distributions of known prognostic covariates in treatment and control group to resemble what would occur had the treatment been randomly assigned. A logistic regression for the treatment group as the dependent variable is performed to obtain the propensity score with the abovementioned matching variables, using all the participants (planned for 174) randomized to the SAR443820 arm and the participants from the historical clinical trial database after filtering as described above. Each participant in the SAR443820 treated group will be matched 1:1 using the Mahalanobis distance to a participant in the historical clinical trial database. Matching will be performed with replacement.

To assess the success of the matching procedure, summary statistics of baseline matching variables will be presented and compared between the two treatment groups before and after matching to assess post-match balance.

Post-matching statistical analysis

Once the matching is performed, the comparison between participants who were randomized to SAR443820 and placebo arm generated from the historical trial database will be provided for the following endpoints using the similar analyses models as described for the primary and secondary endpoints in [Section 3.2.2](#) and [Section 3.3.1.2](#).

- Combined assessment of function and survival (CAFS) score at Week 52, Week 76, and Week 104
- Change from baseline in ALSFRS-R total score to Week 52, Week 76, and Week 104
- Time from baseline to the occurrence of either death or permanent assisted ventilation (>22 hour daily for >7 consecutive days) whichever comes first
- Time from baseline to the occurrence of death

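### The Cox models for death and for death or permanent ventilation leave out age and baseline SVC, which the SAP matches on for the same endpoints elsewhere; adding them is a cheap refinement of small value

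*SAP*

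**What the plan says.** SAP 3.3.1.2, on time-to-event endpoints: "The time to event will be modeled by a Cox proportional hazards model". The covariate list begins "The covariates included in the model are treatment group, randomization strata of the geographic region of the study site, ALS onset region", continues with riluzole, edaravone and sodium phenylbutyrate–taurursodiol use, and ends with "disease duration (from first symptom onset to the screening visit), baseline ALSFRS-R score and baseline NfL". Robust variance estimation is specified. The accompanying log-rank test is stratified by the randomization factors and by baseline NfL split at the median. Neither analysis uses age or SVC.

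SAP 3.4.3 plans an external-control comparison of CAFS, ALSFRS-R change and the same two survival endpoints. It lists age, time since symptom onset, baseline SVC and ALSFRS-R decline rate, and introduces them as factors by which the historical participants are "filtered by the following factors that match our trial eligibility criteria and duration". The next step says "Propensity score matching seeks to balance the distributions of known prognostic covariates in treatment and control group", and a logistic regression "is performed to obtain the propensity score with the abovementioned matching variables".

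Protocol 3.1.1 says of SVC: "The SVC change over time has been demonstrated to be associated with meaningful clinical events, including the time to respiratory insufficiency or death".

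On status, SAP 3.5 says a "hierarchical testing procedure will be applied at a 2-sided 5% significance level for primary and selected secondary endpoints in Part A". The survival endpoints belong to Part B and are not in that sequence.

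**The concern.** The SAP balances its external survival comparison on age and baseline SVC but leaves both out of the randomized comparison of the same endpoints, and gives no reason. Neither variable is a stratification factor, and eligibility is wide (18 to 80 years; SVC at least 60% predicted), so only chance balances them between 174 and 87 participants. Protocol 2.2 names respiratory failure as the usual cause of death, and Protocol 3.1.1 describes SVC as a measure of respiratory muscle strength. Baseline SVC is therefore a plausible predictor of these events.

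If the two variables predict survival beyond what is already in the model, omitting them costs some power, draws the estimated hazard ratio (HR) slightly toward 1, and leaves their chance imbalance unadjusted. Both are available without new data: age at screening, and SVC at screening and on Day 1 before dosing.

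**Working it through.** **Figures in the plan.** The only power statement (Protocol 9.2, SAP 4) is N = 261 for about 80% power on ALSFRS-R change at Week 24. Its placebo change and SD are blacked out, so it cannot be reproduced, and it does not concern survival. There is no survival figure to check. Everything below except the 174 v 87 split and the model specification is an assumption.

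**Model size.** Treatment 1, region (3 levels) 2, onset 1, three background treatments 3, duration 1, ALSFRS-R 1, NfL 1: 10 parameters. At an assumed 50 events that is 50/10 = 5 events per parameter. With age and SVC it is 50/12 = 4.2.

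**Chance imbalance.** The SE of a between-arm difference in a baseline covariate is sqrt(1/174 + 1/87) = 0.131 SD. Assume age SD 11 years, SVC SD 14 points, HR 1.2 to 1.5 per 10 years of age, and HR 0.85 to 0.70 per 10 points of SVC. The SD of the combined predictor is then:

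- weak: sqrt((1.1 × ln 1.2)² + (1.4 × ln 0.85)²) = 0.30
- strong: sqrt((1.1 × ln 1.5)² + (1.4 × ln 0.70)²) = 0.67

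Multiplying by 0.131 gives 0.04 to 0.09 on the log-HR scale. That is an HR factor of 1.04 to 1.09 at 1 SD, and 1.08 to 1.19 at the 95% limit. For scale, SE(log HR) at 50 events is 1/sqrt(50 × 2/3 × 1/3) = 0.30, a 95% factor of exp(1.96 × 0.30) = 1.8.

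**Power, simulated.** 174 v 87, about 50 events, the SAP's full covariate list. Each cell shows power without → with age and SVC. The middle setting lies between the weak and strong ones.

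| Assumed age and SVC effects | HR 0.5 throughout, robust variance (1,500 runs) | HR 0.5 to Week 24, then 1, model-based SE (1,200 runs) | Same, robust variance |
|---|---|---|---|
| weak | 70.9 → 70.8% | 9.6 → 10.0% | 8.8 → 9.2% |
| middle | 66.7 → 68.3% | 9.2 → 9.6% | 9.0 → 8.6% |
| strong | 62.9 → 67.1% | 9.4 → 10.3% | 9.0 → 9.9% |

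A further run with the SAP's covariate count and model-based SEs gave gains of 0 to 5 points under a constant HR of 0.5, and 0 to about 2.5 points when the effect ended at Week 24.

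The low power in the Week 24 scenario agrees with a rough calculation. If events are spread evenly, 24/104 = 23% carry the effect, so the average log HR is 0.23 × ln 0.5 = −0.16. The expected z is 0.16/0.30 = 0.53, which gives power of about 8%.

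**Wider assumptions.** With a true HR of 0.6 and a residual HR per SD of 1.1 to 1.6 for each variable, gains ran as follows:

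- 40 events: 0.2 to 4.1 points
- 80 events: 0.5 to 8.8 points
- 120 events: 0.1 to 11.5 points

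The upper ends need 1.6 per SD for both variables after ALSFRS-R, NfL, onset and duration are accounted for, and a constant effect.

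**Estimate and type I error.** With a true HR of 0.50 and the full list, the mean estimate was 0.489, 0.496 and 0.508 without the two covariates, and 0.481, 0.480 and 0.481 with them. Attenuation was visible only under strong effects and more events (true 0.60, 120 events: 0.639 without, 0.596 with). Null rejection with robust variance was 5.1, 5.7 and 6.1% without, and 5.1, 5.7 and 6.6% with. Across the other null runs with the SAP's covariate count it was about 5 to 8% in both models.

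**The case against.** The strongest reply is that this is a preference about covariates in endpoints on which no confirmatory claim rests. A randomized comparison need not adjust for everything a non-randomized one must balance. Chance imbalance is already reflected in the standard error. The Cox list mirrors the MMRM set, to which disease duration was added on clinical input. ALSFRS-R includes a breathing subdomain and may already carry part of what SVC would add. All of this stands, and it is why the point is minor.

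The design also limits what can be gained. SAP 3.1 keeps the randomized groups in Part B, but placebo participants were to receive SAR443820 from Week 24, and all Part B dosing was paused on 5 December 2023. A constant HR over 104 weeks is therefore optimistic. Partial carry-over of an early effect would fall between the two scenarios.

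Two stronger readings are tempting. One is that the SAP itself declares age and SVC prognostic and then contradicts itself. It does not say so: its wording about prognostic covariates describes matching in general and reaches age and SVC only through the cross-reference to a list introduced as eligibility filters. The Protocol sentence concerns change in SVC, not its baseline value. The other is that the omission biases the HR or forfeits substantial survival power. No documented event count or effect supports that, and at about 50 events the adjusted estimate was no closer to the true value.

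The text of SAP 3.2.3, to which the CAFS rank ANCOVA refers for its prognostic factors, is not visible. Whether age and SVC are adjusted for there cannot be judged.

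**Conclusion.** The omission is real, and the different treatment of the same two endpoints in SAP 3.3.1.2 and 3.4.3 is unexplained. Its consequence is small: some explainable noise stays in two secondary endpoints outside the hierarchy, with no bias in the test and no inflation of type I error.

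At about 50 events the power gain from adding both covariates runs from none to about 5 points under a constant HR of 0.5. It is near zero to about 2.5 points if the effect is limited to Weeks 0 to 24. These figures depend on the assumed event count, treatment effect and residual prognostic strength, none of which the documents give. Larger gains need more events together with strong residual effects. Severity: minor.

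**What to change.** In SAP 3.3.1.2, add age at screening and baseline SVC (% predicted), both continuous, to the Cox covariate list for the two survival endpoints, and keep all other terms. The change reaches the tertiary time-to-event endpoints through SAP 3.4.2. If the sponsor prefers to keep the present model, prespecify the extended one as a sensitivity analysis.

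Do this before Part A database lock. Protocol 6.3 unblinds the sponsor study team, apart from monitors, after that lock, and a later change could look data-driven.

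The cost is one line of text and two more parameters: roughly 4 instead of 5 events per parameter at 50 events, and fewer for death alone. No new data are needed.
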